2.2 Data Summaries

All measured variables and derived parameters will be listed individually and, if appropriate, tabulated by descriptive statistics.

2.3 Continuous

For continuous variables summary tables will be provided giving sample size, arithmetic mean, standard deviation, coefficient of variation (if appropriate), median, minimum and maximum, percentiles and 95% C.I. (Confidence Interval) by study arm for means of variables.

2.4 Categorical

For categorical variables summary tables will be provided giving sample size, absolute and relative frequency and 95% C.I. (Confidence Interval) for proportions by study arm.

2.5 Protocol Deviations

A listing of protocol deviations will be provided within Appendix 16.2.

3. ANALYSIS PLAN

3.1 Introduction

All summaries and analyses documented below will be presented in the final integrated statistical/clinical report and tables that will be based on the E3 guidelines published by ICH. However, it is noted here that no analysis plan prepared in advance of database lock can be absolutely definitive and so the final report may contain additional tables or statistical tests if warranted by the data obtained. The justification for any such additional analyses will be fully documented in the final report.

3.1 Disposition of Subjects

The number of subjects within each analysis population will be summarized. The number of subjects entering each phase of the study will be tabulated along with number of subjects who withdraw. The calculated percentages will be based on the number of subjects in that particular

phase of the study. The phase of the study, timing of withdrawal and reasons for withdrawal will be summarised by treatment (Table 14.1.1).

3.2 Baseline Comparability

3.2.1 Intent

Subject demographics and baseline characteristics will be presented for all subjects within the safety population. The comparability of treatment groups with respect to subject demographics and baseline characteristics will be assessed in a descriptive manner, but no formal statistical testing will be performed.

3.2.2 Variables Considered

Standard continuous or categorical variable summaries will be presented overall and by treatment group for the following variables.

Demography (Table 14.1-3)

- Age at screening visit (years)
- Height and weight at screening
- BMI at screening
- Gender (Male, Female)
- Ethnicity (Hispanic or Latino, Not Hispanic or Latino, Not recorded)
- Race (American Indian or Alaskan Native, Asian, Black or African American, Native Hawaiian/Pacific Islander, White, Other, Not recorded)

Medical History (Tables 14.1-4 to 14.1-5)

- Relevant previous and ongoing medical history (Yes/No).
- Tobacco use history

Separate tabulations will be produced for previous and ongoing conditions using the MedDRA primary system organ class and preferred term (Version 13.1).

Concomitant medications (Tables 14.3.3-11 to 14.3.3-12)

Concomitant medications ongoing at time of first dose of study medication will be coded. Concomitant medications will be coded using the World Health Organization (WHO) Drug

Reference List, which employs the Anatomical Therapeutic Chemical (ATC) classification system.

3.3 Primary Efficacy Endpoint

At week 24, compared to baseline, the mean probing Pocket Depth (PD) reductions (absolute change) for the selected target implant/s will be used as the primary efficacy endpoint. The analysis of the primary endpoint will be based on ITT, mITT, PP and PP2 populations, by-pocket and by-patient analyses.

3.3.1 Principal Analysis

The change in efficacy parameters, PD, during the 24 week treatment, will be modelled using a linear-mixed model (SAS® 9.3 Mixed Procedure) with treatment as fixed factors. Patient and pocket will be entered as random effects. Interactions between treatment and the covariates will be tested and if achieve statistical significance of $\leq 5\%$ will be added to the model as covariate. The analysis will be adjusted to the following covariates known to have influence on the efficacy parameters: age, gender, smoking status, site and baseline measurements. The adequacy of the Mixed Model will be checked and if needed a normalizing transformation will be performed.

Contrasts with 95% C.I. for the difference between the changes by week will be computed.

The Paired T-test or Signed rank test for two means (paired observations) (as is appropriate) will be applied for testing the statistical significance of the decrease in PD at each time point within each study group.

The two-sample T-test or Non-parametric Median test for independent samples (as is appropriate) will be applied for testing the statistical significance of the difference in the PD decrease from baseline between the study groups.

Categorical analysis will be applied for PD change at week 24, using median value calculated overall subjects. Logistic regression will be applied for categorical PD change with adjustment to baseline measure, age, gender, site and smoking status. Interactions between treatment and the covariates will be tested and if found statistically significant, will be added to the model.

Analysis of Variance (ANOVA) will be applied for analysing PD change at week 24, with adjustment to baseline measure, age, gender, site and smoking status. Interactions between treatment and the covariates will be tested and if found statistically significant, will be added to the model.

Missing data will be handled for imputation the primary endpoint data using the MMRM model (Mixed-effect Model for Repeated Measures), which is based on MAR (missing at random) assumption.

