1.5 Primary Efficacy Endpoint

At week 24, compared to baseline, the mean probing Pocket Depth (PD) reductions (absolute change) for the selected target implant/s will be used as the primary efficacy endpoint

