Analysis for the number of pockets with at least 1 mm and at least 2 mm reduction in PD, and analysis for BOP for the target implant/s measured at each visit will be analyzed by a Chi-square test or Fisher's exact test as is appropriate.

Logistic regression will be applied for testing the above differences with adjustment to smoking status, GI, medical center and other suspected confounders, if found. Odds Ratio and 95% Confidence Interval will be calculated using the Logistic model.

Similar mixed models for PD, R and RAL with time as a fixed repeated covariate will be used to reveal the changes of these parameters over time.

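### The principal mixed model in SAP 3.3.1 does not match the week-24 primary endpoint: it lists no visit or treatment-by-visit term, yet promises by-week contrasts

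*SAP*

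**What the plan says.** The endpoint is fixed at one time point. SAP 3.3 (and 1.5) defines it as "At week 24, compared to baseline, the mean probing Pocket Depth (PD) reductions (absolute change) for the selected target implant/s".

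The first paragraph of SAP 3.3.1 describes the model for PD change over the whole 24-week treatment period:

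- Fixed part: the change "will be modelled using a linear-mixed model (SAS® 9.3 Mixed Procedure) with treatment as fixed factors".
- Random part: "Patient and pocket will be entered as random effects".
- Adjustment: "covariates known to have influence on the efficacy parameters: age, gender, smoking status, site and baseline measurements".
- Interactions: "Interactions between treatment and the covariates will be tested and if achieve statistical significance of" 5% or less, they are added. Visit is not one of the listed covariates.

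The next paragraph adds: "Contrasts with 95% C.I. for the difference between the changes by week will be computed".

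Further down, 3.3.1 also lists a logistic regression of dichotomised week-24 change, a covariate-adjusted ANOVA of week-24 change, and an MMRM for missing primary data, with no terms or covariance given. A model that does contain time appears in 2.1 and again in 3.5: "Similar mixed models for PD, R and RAL with time as a fixed repeated covariate". Its stated purpose is to show how the parameters change over time, and no treatment-by-time term is named there either. SAP Appendix I (Table 14.2-1) shows that PD is summarised at baseline and weeks 8, 12, 16 and 24.

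**The concern.** A mixed model with one treatment term and no visit term has one treatment coefficient. Fitted to several post-baseline visits, that coefficient pools the effect over all of them, whereas the endpoint is the effect at the last one. By-week contrasts need a treatment-by-week term or a separate fit per week, and neither is stated. The interaction rule cannot supply the term, because it covers only treatment with the listed covariates.

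The time course matters in this trial. SAP 1.2 has chips inserted every fortnight for the first 12 weeks, and the endpoint is read at week 24, 12 weeks later. The effect may still be building or may have faded by then. SAP 3.5 itself lists PD at weeks 12 and 16 against week 24 as an exploratory question. A pooled coefficient could understate a late benefit, or reach significance on an early benefit that has gone by week 24. Several analyses of the primary endpoint are listed without saying which one decides, so the pooled model and the week-24 ANOVA could disagree with no rule for choosing.

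**Working it through.** **1. Which data does the model text point to?** Three features suggest repeated visits in one fit.

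- The model paragraph speaks of change over a period, while the logistic and ANOVA paragraphs of the same section specify week 24.
- A pocket random effect can be separated from residual error only if each pocket contributes more than one visit.
- The model with time is described separately.

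One feature points the other way: the by-week contrasts imply a week term or per-week fits. The text does not settle it.

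**2. Planning figure (SAP 1.8).** Inputs: difference 0.50 mm, SD 1.30 mm, two-sided 0.05, two-group t-test, 85% power. The exact t calculation gives n = 122.36, so 123 per arm, and power at 123 per arm is 85.2%. The plan's figure reproduces. It is a single-time-point calculation, which fits a week-24 comparison.

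**3. What the listed terms estimate if weeks 8, 12, 16 and 24 are pooled.** With complete data and equal correlation ρ between visits:

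- Treatment coefficient = (d8 + d12 + d16 + d24) / 4.
- SD of a patient's mean over four visits = 1.30 × √((1 + 3ρ) / 4).
- ρ = 0.5: 1.30 × √0.625 = 1.028 mm.
- ρ = 0.7: 1.30 × √0.775 = 1.144 mm.

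The documents give neither visit-specific effects nor ρ. The profiles and the range 0.5-0.7 are assumptions. SD 1.30 at every visit, 123 per arm and one pocket per patient are used throughout. Power is from the two-sample t-test.

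| Assumed effect at weeks 8/12/16/24 (mm) | Pooled effect (mm) | Week-24 effect (mm) | P(significant), pooled, ρ = 0.5 | P(significant), pooled, ρ = 0.7 | P(significant), week-24 test |
|---|---|---|---|---|---|
| 0.5/0.5/0.5/0.5 | 2.0/4 = 0.50 | 0.50 | 96.7% | 92.7% | 85.2% |
| 0.2/0.3/0.4/0.5 | 1.4/4 = 0.35 | 0.50 | 75.8% | 66.6% | 85.2% |
| 0.6/0.6/0.5/0.0 | 1.7/4 = 0.425 | 0.00 | 89.8% | 82.7% | 5% (the two-sided level) |

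**4. Check by simulation.** Sixty simulated trials per profile (123 per arm, one pocket per patient, ρ = 0.5) were fitted with and without treatment-by-visit. The true week-24 effect was 0.50 mm in all three profiles.

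| Profile | Model with treatment only | Week-24 contrast, model with treatment-by-visit |
|---|---|---|
| Linear growth from 0 at week 0 to 0.50 at week 24 (four-visit mean 0.3125) | 0.31 | 0.51 |
| 0.7/0.7/0.6/0.5 (mean 0.625) | 0.63 | 0.51 |
| Constant 0.50 | 0.50 | 0.49 |

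The treatment-only model returns the four-visit mean. The model with treatment-by-visit returns the week-24 effect.

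**5. If only week-24 data enter.** The treatment coefficient is then the week-24 effect and nothing is averaged. The pocket random effect is then not separable from the residual, and by-week contrasts would need one fit per week. The SAP states neither.

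**The case against.** A reader might infer that the trial's primary analysis will in fact estimate an effect averaged over weeks 8-24. The documents do not support that as a fact. SAP 3.3.1 never says that all visits enter one fit. The by-week contrasts suggest that week belongs in the analysis and that the term list is abbreviated. The endpoint is set at week 24 in 1.1, 1.5 and 3.3, and all eight primary tables (14.2-2.1 to 14.2-2.8) are titled as change at week 24. A covariate-adjusted ANOVA of week-24 change is listed in the same section, with an MMRM for missing data. SAP 3.5 also says that the methods set out below it serve the primary and secondary endpoints, and the model with time is among them. A week-24 estimate is therefore planned.

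A reader might also take the unfavourable figures as expected losses. They are not: the building and waning profiles are hypothetical. If the effect is constant, pooling causes no bias and has more power than planned.

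These points limit the finding but do not remove it. The listed terms still conflict with the promised contrasts. The model with time names no treatment-by-time term, the MMRM has no stated terms, and the ANOVA is one of several analyses with none named as confirmatory. An intended week term has to be inferred, and a programmer following the paragraph literally would leave it out.

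**Conclusion.** Wrong as written. The term list of the principal model is inconsistent with the week-24 endpoint and with the by-week contrasts in the same section, and the SAP does not say which visits enter or which result is confirmatory. Averaging over visits is a consequence only if the listed terms are fitted to weeks 8, 12, 16 and 24 together.

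In that case, with SD 1.30 mm, 123 per arm and an assumed correlation of 0.5-0.7, the result depends on the time course:

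- Constant 0.50 mm: no bias, 93-97% power.
- Building to 0.50 mm at week 24: a pooled effect of 0.35 mm and 67-76% power, against 85% planned.
- Waning to nothing at week 24: an 83-90% chance of a significant result.

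Nothing in the documents says which profile to expect.

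**What to change.** In SAP 3.3.1, do one of the following.

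- **Repeated-measures route.** State that weeks 8, 12, 16 and 24 enter. Add visit and treatment-by-visit to the stated covariates. State the within-pocket covariance over visits (for example unstructured) and how two pockets in one patient are allowed for. Name the week-24 treatment contrast from this model as the single primary test. The by-week contrasts then come from the same fit.
- **Single-time-point route.** Name the already listed covariate-adjusted ANOVA of week-24 change as the primary test, and describe the mixed model as supportive.

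Either way, label the remaining analyses in 3.3.1 as supportive. The cost is SAP wording and, for the first route, one changed model statement. No new data are needed. The sample size stays as it is, because 123 per arm already gives about 85% power for a 0.50 mm difference at week 24.

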2. STATISTICAL METHODS

2.1 General

The change in efficacy parameters, PD, R and RAL during the 24 week treatment, will be modelled using a linear-mixed model (SAS® 9.3 Mixed Procedure) with treatment as fixed factors. Patient and pocket will be entered as random effects. The treatment-by-center interaction will be tested and if achieve statistical significance of $\leq 5\%$ will be added to the model as covariate. The analysis will be adjusted to the following covariates known to have influence on the efficacy parameters: age, gender, smoking status and baseline measurements. The adequacy of the Mixed Model will be checked and if needed a normalizing transformation will be performed. This model will be used for the reduction in PD, R and for improvement in RAL.

Contrasts with 95% Confidence Interval (C.I.) for the difference or ratio between the changes will be computed.

The Paired T-test or Signed rank test for two means (paired observations) (as is appropriate) will be applied for testing the statistical significance of the decrease in PD at each time point within each study group.

The two-sample T-test or Non-parametric Wilcoxon-Mann-Whitney Rank sum test for independent samples (as is appropriate) will be applied for testing the statistical significance of the difference in the percent PD decrease from baseline between the study groups.

Patients may have multiple pockets being treated. All treated pockets will be taken into account to create a by-pocket analysis in addition to the by-patient analysis.

Corresponding 95% C.I. for the difference between treatments not including zero for linear model, or 95% C.I. for the ratios between treatments not including unity for the log-linear regression will prove superior to treatment with PerioChip® versus Subgingival debridement.

Analysis for the number of pockets with at least 1 mm and at least 2 mm reduction in PD, and analysis for BOP for the target implant/s measured at each visit will be analyzed by a Chi-square test or Fisher's exact test as is appropriate.

Logistic regression will be applied for testing the above differences with adjustment to smoking status, Gingival Index (GI), medical center and other suspected confounders, if found. Odds Ratio and 95% Confidence Interval will be calculated using the Logistic model.

Similar mixed models for PD, R and RAL with time as a fixed repeated covariate will be used to reveal the changes of these parameters over time.

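### SAP 3.3.1 lets treatment-by-covariate interactions enter the principal PD model on a 5% pre-test without saying how the treatment effect is then read, and SAP 2.1 and 3.5 give different models for the same endpoint

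*SAP*

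**What the plan says.** SAP 3.3.1 models PD change with a linear mixed model, with patient and pocket as random effects, adjusted for "age, gender, smoking status, site and baseline measurements". Then: "Interactions between treatment and the covariates will be tested and if achieve statistical significance of" 5% or less, they join the model. For the median-split logistic regression and the week-24 ANOVA in the same section the rule recurs, with no level stated: "Interactions between treatment and the covariates will be tested and if found statistically significant, will be added to the model". On the estimate itself, 3.3.1 says only: "Contrasts with 95% C.I. for the difference between the changes by week will be computed". SAP 2.1 makes the superiority decision rest on whether the 95% CI for the treatment difference excludes zero.

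Two other sections describe a model for the same endpoint:

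| SAP section | Covariates | Interactions tested |
|---|---|---|
| 3.3.1 | age, gender, smoking, site, baseline | treatment by each of the five |
| 2.1 | age, gender, smoking, baseline | "The treatment-by-center interaction will be tested and if achieve statistical significance of" 5% or less it is added; no center main effect is listed |
| 3.5 | age, gender, smoking, baseline | treatment by each of the four |

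Section 3.5 is headed as exploratory but states that its methods serve the primary and secondary endpoints. No section says which text prevails.

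**The concern.** Once a treatment-by-covariate interaction is in the model, the treatment difference is no longer a single number. It varies with the covariate, so the estimate and CI depend on where, or with what weights, the difference is evaluated. The SAP fixes in advance that the model may change but not how the result is then read. Two analysts following 3.3.1 faithfully could report different confirmatory estimates from the same data, and the choice could be made after seeing them.

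The differing lists in 2.1 and 3.5 add a second layer. Besides the interaction rule, they disagree on whether site is adjusted for at all, although site is a randomization stratification factor (Protocol, summary of changes from version 1 to version 2, Randomization Code).

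**Working it through.** **Inputs from the documents.** 123 patients per arm, difference 0.50 mm, SD 1.30 mm, two-sided 5% (SAP 1.8). Five covariates and 5% entry (SAP 3.3.1). At least nine sites (Protocol, summary of changes to version 8, Number of patients).

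**The plan's own figure.** A two-sample t-test with 123 per arm, 0.50 mm and SD 1.30 has 85.2% power. With 15% drop-out, 246/0.85 = 289.4, so 290 randomized. Both reproduce.

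**Chance that the model changes with no true interaction**, for independent tests at 5%:
- 3.3.1, five tests: 1 - 0.95^5 = 22.6% (simulated 21.9-23.5%)
- 3.5, four tests: 1 - 0.95^4 = 18.5%
- 2.1, one test: 5%

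*Baseline measurements* is plural, so five is a minimum.

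**Three readings the text allows.** With interactions in the model, the treatment difference at covariate values x is b + g·x, where b is the treatment coefficient and g the interaction coefficients.
- Observed weights: x set to the sample means.
- Equal weights: every category counted equally.
- Raw coefficient: b alone, which is the difference at age 0, baseline PD 0 mm and the reference categories if covariates are not centred.

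**How far equal weights can move the estimate, by hand.** Take smoking, by patient, with 25% smokers (assumed). There are 246 × 0.25/2 = 30.75 smokers and 92.25 non-smokers per arm. SE(g) = 1.30 × √(2/30.75 + 2/92.25) = 0.383 mm, so an interaction that just reaches 5% has |g| = 1.96 × 0.383 = 0.75 mm. Equal and observed weights then differ by (0.50 - 0.25) × 0.75 = 0.19 mm, or 38% of 0.50 mm. The same steps give 0.32 mm with 15% smokers (SE 0.464) and 0.10 mm with 35% (SE 0.348). In simulation, when any interaction enters, the equal-weight estimate moves by 0.05 mm on average, with 90th percentile 0.19 mm (0.10-0.31 mm for 35-15% smokers). With observed weights the average move is 0.003 mm.

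**Simulated operating characteristics.** 246 patients, nine centers, 8,000 trials per scenario (Monte Carlo SE about 0.24 points at 5%). Each interaction is tested singly and all significant ones are added. Assumed: age 60 (SD 10), 50% female, 25% smokers, baseline PD 5/6/7/8 mm at 40/30/20/10%, no true interactions, no missing data.

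| Reading | Type I error | Power at 0.50 mm |
|---|---|---|
| No pre-test | 4.6-5.1% | about 83% |
| Observed weights | 4.7-5.1% | about 83% |
| Equal weights | 5.3-5.5% (about 6-7% with 15% smokers) | about 1 point lower |
| Raw coefficient, uncentred | 13.6-15.0% | 76-77% |

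These come from a by-patient week-24 linear model. For equal weights, the upper end of the main range and the power loss come from a repeated-measures version with patient and pocket random effects. The raw coefficient does badly because, far outside the data, b is almost a multiple of the interaction slope that was selected for being significant. Its median SE when an interaction enters is 0.52-0.53, against about 0.17 for the averaged effect.

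**Share of all null trials whose significance changes.** In the repeated-measures version, significance differs from the no-pre-test model in 7.2% of trials where an interaction enters under equal weights (3.4-10.2% for 35-15% smokers), and in 0.3% under observed weights. Equal weights: 0.226 × 7.2% = 1.6% of all trials (0.226 × 3.4% = 0.8% to 0.226 × 10.2% = 2.3%). Observed weights: 0.226 × 0.3% = 0.07%.

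**The case against.** **The effect is small.** With observed weights the pre-test changes almost nothing, and with equal weights significance changes in under 2% of null trials in the main scenario. That stands. A reader might infer from the 14-15% figure that the plan carries a large false-positive risk. The documents do not support this: they nowhere say the raw coefficient will be read, and the figure depends on how covariates are coded. It shows how wide the unspecified choice is and does not predict what the sponsor would do.

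**Section 3.3.1 is the most specific text and would prevail.** Probably, but the main gap lies inside 3.3.1, and 3.5 expressly claims the primary endpoint.

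**Site may not mean clinical center.** The SAP also uses *sites* for the four pocket aspects. Clinical center is the likelier reading because it is a stratification factor, but this is an inference. The nine-level term in the simulation and the comparison with 2.1 rest on it.

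**The week-24 contrast.** A reader might infer that 3.3.1 cannot produce one, since it lists no week or treatment-by-week term. That goes too far. The section calls for contrasts by week, adds "Missing data will be handled for imputation the primary endpoint data using the MMRM model (Mixed-effect Model for Repeated Measures"), and specifies a week-24 ANOVA. Section 2.1 provides "Similar mixed models for PD, R and RAL with time as a fixed repeated covariate". The model could also be fitted visit by visit. The route is ambiguous, not absent, and refitting at week 24 alone leaves the interaction result unchanged.

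**The protocol may settle it.** Only its summary of changes was available, so its full statistical section could not be checked.

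**Conclusion.** The point holds as a pre-specification gap that should be closed. A stated data-driven rule can alter the principal model in about 22-23% of trials with no true interaction, and the SAP does not say how the confirmatory difference and CI are then obtained. The consequence ranges from negligible (observed weights) through small (equal weights) to serious (raw coefficient, uncentred). The harm is modest unless the last reading is used. Separately, 2.1 and 3.5 give models for the primary endpoint that differ from 3.3.1.

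The 22.6% needs only five roughly independent 5% tests. The error rates, power and shifts rest on the assumed covariate distributions and are indicative. The 83% power is that of the simulated adjusted model, not a correction of the SAP's 85%.

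**What to change.** Make 3.3.1 the single primary-endpoint model and have 2.1 and 3.5 refer to it.

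- Fixed effects: treatment, visit, treatment-by-visit, baseline PD, clinical center (named as such), smoking, age and gender. Keep the patient and pocket random effects, and state the covariance over visits.
- Name the week-24 treatment contrast and its 95% CI from this model as the confirmatory result.
- Let no treatment-by-covariate interaction enter this model, the week-24 ANOVA or the logistic model. Report interactions separately as exploratory.
- If interactions are to be kept, state in advance that the treatment effect is averaged over the observed covariate distribution. That sentence alone removes most of the problem.

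The cost is SAP wording; the sample size does not change. A true interaction would appear only in the exploratory report. Center terms are new only relative to 2.1 and 3.5 (about 8 degrees of freedom with nine centers) and cost well under one point of power even if center explains nothing.

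This does not settle the primary population, by-pocket versus by-patient analysis (SAP 3.3), or the optional normalizing transformation in 3.3.1. Each needs its own decision.
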